4.6.3 Study Discontinuation

The Sponsor has the right to terminate this study at any time. Reasons for terminating the study may include, but are not limited to, the following:

- The incidence or severity of adverse events in this or other studies indicates a potential health hazard to patients
- Patient enrollment is unsatisfactory

The Sponsor will notify the investigator if the Sponsor decides to discontinue the study.

4.6.4 Site Discontinuation

The Sponsor has the right to close a site at any time. Reasons for closing a site may include, but are not limited to, the following:

- Excessively slow recruitment
- Poor protocol adherence
- Inaccurate or incomplete data recording
- Non-compliance with the International Council for Harmonisation (ICH) guideline for Good Clinical Practice
- No study activity (i.e., all patients have completed the study and all obligations have been fulfilled)

5. ASSESSMENT OF SAFETY

5.1 SAFETY PLAN

Azithromycin is an approved agent to treat patients with a bacterial infection, and the safety profile for both acute and chronic dosing is well characterized in the drug manufacturer's prescribing information. The use of HP ¹²⁹Xe MR imaging is an investigational diagnostic tool. While there is clinical experience with ¹²⁹Xe MRI in studies with healthy volunteers, COPD patients, and patients with other chronic lung diseases, its safety profile has not been fully characterized.

The safety plan for this study is designed to ensure patient safety and includes specific eligibility criteria, a Safety Monitoring Committee (SMC), and specific pharmacovigilance monitoring assessments, as detailed below.

A SMC will be used to carefully review the accumulating safety data. The SMC will consist of Sponsor representatives from the following functions: clinical science, drug

safety, biostatistics, and statistical programming and analysis (SPA), and the principal investigator or delegate from each participating clinical study site. The SMC will regularly monitor the safety of the patients in the study and review cumulative data approximately every 6 months.

The anticipated important safety risks are outlined below.

5.1.1 Risks Associated with ^{129}Xe

5.1.1.1 General Anesthesia

Xenon is a general anesthetic when breathed continuously at concentrations >70% for extended periods of time. Patients may experience transient effects including dizziness, tingling or numbness of the extremities, nausea, smelling of flowers, or a feeling of well-being and euphoria.

Adverse effects may include those listed below and will be monitored closely by medically trained staff throughout the imaging session.

- Sense of analgesia (dizziness, light-headedness, numbness, euphoria, sleepiness, and tingling in extremities)
- Altered heart rate
- Altered gas exchange, SpO_2

5.1.1.2 Hypoxemia

The effect of xenon on the respiratory tract has been the subject of many animal studies. Results showed moderately increased airway resistance with high xenon concentrations (70%) in pigs and dogs with or without methacholine-induced bronchoconstriction (Calzia et al. 1999a), but no effects were seen at a lower xenon concentration (50%) in dogs (Zhang et al. 1995). In a study in pigs (Baumert et al. 2005), where the resistance was corrected for gas viscosity and density, it was concluded that the increase in airway pressure observed in xenon anesthesia can be attributed entirely to its high density and viscosity, and that xenon does not exert any major effects on airway diameter.

Diffusion hypoxia manifests as a reduction in alveolar oxygen partial pressure and occurs when the administration of the gas mixture is discontinued and room air is breathed. This phenomenon is seen in anesthesia with nitrous oxide (N_2O) and depends on lipid solubility of the gas. As the solubility of xenon is higher than that of N_2 , this could theoretically occur after exposure to xenon gas. A study in pigs has been performed to address this question and the arterial partial oxygen pressure was measured during nitrogen wash-in (30% O_2 and 70% N_2) after an initial 30-minute ventilation period with either 70% xenon and 30% O_2 , or 70% N_2O and 30% O_2 . The changes in arterial partial oxygen pressure were much less in the xenon-treated pigs as compared to that of the N_2O group, demonstrating that diffusion hypoxia is much less likely with xenon than with N_2O , probably due to the low blood solubility of the noble gas (Calzia et al. 1999a).

5.1.2 Risks Associated with Azithromycin

Summary data from Phase III and Phase IV trials indicate that azithromycin is generally well tolerated. The most common adverse events observed were gastrointestinal disorders followed by central nervous system (hearing loss) disorders, and all were typically mild to moderate. Decreased hearing has been reported at low frequency and was reversible. Prolongation of QT interval and cases of torsades de pointes have been reported, with greater incidence in elderly patients.

5.1.2.1 Hypersensitivity

As with erythromycin and other macrolides, serious allergic reactions including angioneurotic edema and anaphylaxis (rarely fatal), Acute Generalized Exanthematous Pustulosis (AGEP), and Drug Reaction with Eosinophilia and Systemic Symptoms (DRESS) have been reported. Some of these reactions with azithromycin have resulted in recurrent symptoms and required a longer period of observation and treatment.

5.1.2.2 Hepatotoxicity

Since the liver is the principal route of elimination for azithromycin, the use of azithromycin should be undertaken with caution in patients with significant hepatic disease. Cases of fulminant hepatitis potentially leading to life-threatening liver failure have been reported with azithromycin. Some patients may have had preexisting hepatic disease or may have been taking other hepatotoxic medicinal products.

In case of signs and symptoms of liver dysfunction, such as rapid developing asthenia associated with jaundice, dark urine, bleeding tendency or hepatic encephalopathy, liver function tests/investigations should be performed immediately. Azithromycin administration should be stopped if liver dysfunction has emerged.

5.1.2.3 Ergot Derivatives

In patients receiving ergot derivatives, ergotism has been precipitated by co-administration of some macrolide antibiotics. There are no data concerning the possibility of an interaction between ergot and azithromycin; however, because of the theoretical possibility of ergotism, azithromycin and ergot derivatives should not be co-administrated.

5.1.2.4 Superinfection

As with any antibiotic preparation, observation for signs of superinfection with non-susceptible organisms including fungi is recommended.

5.1.2.5 *Clostridium difficile* Associated Diarrhea

Clostridium difficile associated diarrhea (CDAD) has been reported with the use of nearly all antibacterial agents, including azithromycin, and may range in severity from mild diarrhea to fatal colitis. Strains of *C. difficile* producing hypotoxin A and B contribute to the development of CDAD. Hypotoxin-producing strains of *C. difficile* cause increased morbidity and mortality, as these infections can be refractory to antimicrobial therapy and

may require colectomy. Therefore, CDAD must be considered in patients who present with diarrhea during or subsequent to the administration of any antibiotics. Careful medical history is necessary since CDAD has been reported to occur over 2 months after the administration of antibacterial agents. Patients who develop *C. difficile* diarrhea during the study will be discontinued from treatment.

5.1.2.6 Myasthenia Gravis

Exacerbations of the symptoms of myasthenia gravis and new onset of myasthenia syndrome have been reported in patients receiving azithromycin therapy.

5.1.2.7 Tinnitus or Hearing Loss

Hearing disturbances including hearing loss, deafness and/or tinnitus, and reports of taste/smell perversion and/or loss have been reported in postmarketing surveillance and in randomized controlled trials assessing benefit/risk profile of azithromycin to prevent AEx in COPD (Albert et al. 2011).

Patients in Cohort A will complete the *HHIE-S* (see [Appendix 7](#)) to assess perceived hearing disability. Those with *known significant hearing impairment at screening will be excluded*. Patients who are randomized to the azithromycin arm complaining of worsening tinnitus, *onset hearing loss*, or worsening hearing loss *will permanently discontinue azithromycin and be referred for formal audiology testing*.

5.1.2.8 Elevated Liver Enzymes

Abnormal liver function, hepatitis, cholestatic jaundice, hepatic necrosis, and hepatic failure have been reported, some of which have resulted in death. The combination of transaminase elevations and elevated bilirubin without evidence of obstruction is generally recognized as an important predictor of severe liver injury that could lead to death or the need for liver transplants in some patients. Discontinue azithromycin immediately if signs and symptoms of hepatitis occur.

Conduct liver function tests (ALT, AST, and bilirubin) prior to the initiation of therapy with azithromycin in all patients, then every 12 weeks thereafter. Dosage modifications or interruption may be necessary for liver enzyme elevations. These guidelines should be followed for any patient who may initiate azithromycin treatment, whether as prevention or rescue therapy.

5.1.2.9 Hypersensitivity: Rash, Pruritus, Tongue, or Facial Swelling

The only contraindication listed in the E.U. Summary of Product Characteristics for azithromycin is giving it to patients with known hypersensitivity to macrolide antibiotics.

5.1.2.10 Prolongation of QT Interval

Prolonged cardiac repolarization and QT interval, imparting a risk of developing cardiac arrhythmia and torsades de pointes, have been seen with treatment with macrolides, including azithromycin. Cases of torsades de pointes have been spontaneously reported during postmarketing surveillance in patients receiving azithromycin.

Physician/Principal Investigators should consider the risk of QT prolongation, which can be fatal when weighing the potential risks and benefits of azithromycin for patients have one or more contraindications

- Known prolongation of the QT interval, a history of torsades de pointes, congenital long QT syndrome, bradyarrhythmias or uncompensated heart failure
- Co-medications known to prolong the QT interval
- Ongoing proarrhythmic conditions such as uncorrected hypokalemia or hypomagnesemia, clinically significant bradycardia, and in patients receiving Class IA (quinidine, procainamide) or Class III (dofetilide, amiodarone, sotalol) antiarrhythmic

ECG testing will be performed during the screening and baseline visits to exclude patients with known risk associated with QT prolongation. ECG testing should be repeated every 6 months to monitor for any significant changes in the QT interval months.

5.1.3 Management of Patients Who Experience Adverse Events

5.1.3.1 Dose Modifications

Reduction in dosing for adverse events is not permitted. Patients who experience certain adverse events considered to be related to study drug should be discontinued from treatment as described in Section 4.6.1.

5.1.3.2 Treatment Interruption

Study treatment may be temporarily suspended in patients who experience toxicity considered to be related to study drug. If study treatment has been withheld for two or more consecutive dosing visits because of toxicity, the patient should be discontinued from study treatment. However, if the adverse event(s) that led to withholding dosing shows clear evidence of improvement in the investigator's judgment, treatment may be resumed; the Medical Monitor may be consulted as appropriate.

5.1.3.3 Management Guidelines

Guidelines for management of specific adverse events are outlined in [Table 1](#).

Table 1 Management Guidelines

Event	Action to Be Taken
Hepatotoxicity	
ALT or AST $>3 \times$ ULN in combination with total bilirubin $>2 \times$ ULN or clinical jaundice	
 Immediately discontinue study treatment. Elevations of AST or ALT of $>5 \times$ ULN should be reported as adverse event(s) of special interest to the Sponsor in an expedited manner (see Section 5.3.3). A hepatology consult is recommended.
Hearing Disturbances	
Any reported onset hearing loss, worsening hearing loss, or hearing disturbance	
 Discontinue study treatment. Refer for formal audiology testing.
QT Prolongation	
Sustained (at least two ECG measurements >30 minutes apart) QTcF that is >500 ms and >60 ms longer than the baseline value	
 Unless there is a clear alternative cause other than study drug, discontinue study treatment (see Section 5.1.3.4).^a
Sustained absolute QTcF that is >515 ms	
 Unless there is a clear alternative cause other than study drug, discontinue study treatment (see Section 5.1.3.4).^a
An episode of torsades de pointes or a new ECG finding of clinical concern	
 Unless there is a clear alternative cause other than study drug, discontinue study treatment (see Section 5.1.3.4).^a

ULN=upper limit of normal.

^a In rare circumstances, it may be acceptable to resume azithromycin, provided that any ECG abnormalities have resolved and the patient is appropriately monitored, following discussion with the Medical Monitor. Clinical judgment should be applied.

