4.1.2 Exclusion Criteria

Patients who meet any of the following criteria will be excluded from study entry:

- History of allergy or hypersensitivity to azithromycin
- Significant known respiratory disorders other than COPD that, in the view of the investigator, will affect the trial
- A COPD exacerbation and/or pneumonia within the 4 weeks prior to screening (Visit 1)
- FEV₁ percent predicted less than 25%
- Pregnant or breastfeeding, or intending to become pregnant during the study period (all patients) or within 28 days after the final dose of azithromycin (patients enrolled in Cohort A receiving azithromycin)

Women of childbearing potential must have a negative serum pregnancy test result at screening.

- Participation in an interventional clinical trial within 4 weeks of screening (Visit 1) or receipt of any investigational medicinal product (IMP) within 30 days or 5 half-lives, whichever is longer
- Use of systemic corticosteroids within 4 weeks (oral or IV) or 12 weeks (intramuscular [IM]) prior to screening
- Active tuberculosis requiring treatment within 12 months prior to Visit 1

Patients who have completed treatment for tuberculosis at least 12 months prior to Visit 1 and have no evidence of recurrent disease are permitted.
- Receiving treatment considered to be palliative (life expectancy <12 months)
- Myocardial infarction, unstable angina, or stroke within 12 months prior to screening (Visit 1)
- Clinically significant ECG changes, which in the opinion of investigator warrants further investigation or with a QTc interval > 450 ms
- History of congenital or documented QT prolongation
- Currently receiving treatment with other active substance at doses known to prolong QT interval such as antiarrhythmic of Classes Ia and III, cisapride, and terfenadine
- Electrolyte disturbance (e.g., clinically significant hypokalemia or hypomagnesemia)
- Clinically relevant bradycardia, cardiac arrhythmia, or severe cardiac insufficiency
- History of myasthenia gravis
 - For patients in Cohort A: Known *significant hearing impairment as indicated by a score of ≥ 26 on the Hearing Handicap Inventory in the Elderly—Screening Questionnaire (HHIE-S) or as determined by the investigator*
- Impaired hepatic function
- Severe renal insufficiency (estimated glomerular filtration rate [eGFR] <10 mL/min)
- Concomitant use of ergot derivatives
- Bloodborne infection (e.g., HIV, hepatitis B or C)
- History of *Clostridium difficile* (*C. difficile*) diarrhea

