4.6 TREATMENT, PATIENT, STUDY, AND SITE DISCONTINUATION

4.6.1 Study Treatment Discontinuation

Patients must permanently discontinue study treatment if they experience any of the following:

- Any medical condition that the investigator or Sponsor determines may jeopardize the patient's safety if he or she continues to receive study treatment

- Investigator or Sponsor determination that treatment discontinuation is in the best interest of the patient
- Any Grade 4 adverse event that the investigator determines to be related to study treatment

This excludes COPD exacerbations, unless they meet one of the other criteria for study treatment discontinuation.
- Pregnancy
- Development of *C. difficile* diarrhea (*for patients in Cohort A randomized to azithromycin*)
- *Any onset hearing loss, worsening hearing loss, hearing disturbance, or decline in the interpretation of the HHIE-S score (for patients in Cohort A randomized to azithromycin)*

The primary reason for study treatment discontinuation should be documented on the appropriate eCRF. Patients who discontinue study treatment will not be replaced.

Patients will return to the clinic for scheduled study visits after the final dose of study drug (see [Appendix 1](#) for additional details).

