5.3.3 Assessment of Severity of Adverse Events

The WHO toxicity grading scale (see Appendix 5) will be used for assessing adverse event severity. Table 2 will be used for assessing severity for adverse events that are not specifically listed in the WHO toxicity grading scale.

Table 2 Adverse Event Severity Grading Scale for Events Not Specifically Listed in WHO Toxicity Grading Scale

Grade	Severity
1	Mild; transient or mild discomfort (<48 hours); no medical intervention or therapy required
2	Moderate; mild to moderate limitation in activity; some assistance may be needed; no or minimal medical intervention or therapy required
3	Severe; marked limitation in activity; some assistance usually required; medical intervention or therapy required; hospitalization possible
4	Life-threatening; extreme limitation in activity; significant assistance required; significant medical intervention or therapy required, hospitalization or hospice care probable

WHO=World Health Organization.

Notes: Developed by the Division of Microbiology and Infectious Diseases.

Regardless of severity, some events may also meet seriousness criteria. Refer to definition of a serious adverse event (see Section [5.2.2](#)).

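### For a treated torsades de pointes episode with no clear alternative cause, Section 4.6.1 makes the azithromycin stop permanent, Table 1 footnote a leaves resumption open, and nothing says which prevails

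*Combined protocol and SAP*

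**What the plan says.** Table 1 in Section 5.1.3.3 has three rows under QT prolongation. The third is "An episode of torsades de pointes or a new ECG finding of clinical concern". The action for each row is "Unless there is a clear alternative cause other than study drug, discontinue study treatment", and each action carries footnote a: "In rare circumstances, it may be acceptable to resume azithromycin, provided that any ECG abnormalities have resolved". The footnote also asks for appropriate monitoring, discussion with the Medical Monitor and clinical judgment. It sets no limit by grade, by relatedness or by row.

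Section 4.6.1 opens with "Patients must permanently discontinue study treatment if they experience any of the following". One item on its list is "Any Grade 4 adverse event that the investigator determines to be related to study treatment". The only exception attached to that item is for COPD exacerbations. The list has no separate QT or arrhythmia item.

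Three other sections bear on the point:

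- Section 5.1.3.1 refers to Section 4.6.1 for discontinuation after certain drug-related events.
- Section 5.1.3.2 lets treatment be suspended for drug-related toxicity and resumed once the investigator sees clear improvement. Consulting the Medical Monitor is optional, and no grade is excluded.
- Section 5.1.3.4 repeats the three QT triggers and says azithromycin should be discontinued. It neither calls the stop permanent nor mentions resumption.

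**The concern.** Footnote a hangs on the instruction to discontinue, and that instruction applies when no other cause is clear. The permission to resume is therefore aimed at the cases in which azithromycin remains the suspected cause. If such a case is also Grade 4, Section 4.6.1 has already closed the question with a mandatory permanent stop.

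This is a matter of patient safety. Section 5.1.2.10 acknowledges that QT prolongation can be fatal. A site managing such an event would find a prohibition in one section and a conditional permission in another, at a moment when the instruction ought to be unambiguous.

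**Working it through.** No arithmetic decides this point. The check is whether one event can satisfy the conditions of both rules at once.

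1. **Which patients footnote a covers.** Resuming presupposes stopping. Table 1 stops treatment for torsades only where no alternative cause is clear, so the footnote reaches those patients. Nothing in it removes torsades, related events or Grade 4 events.
2. **Relatedness.** Table 3 (Section 5.3.4) treats an event as related unless there is evidence of another etiology or no plausible timing. An arrhythmia during daily azithromycin has plausible timing. With no evidence of another cause it is related by default. The two tests are worded differently: some evidence of another cause might lead an investigator to judge the event unrelated even though that cause is not clear. The overlap is large but not complete.
3. **Grade.** On the cardiac rhythm row of Appendix 5, a transient asymptomatic event without treatment is Grade 2, a recurrent or persistent one without treatment is Grade 3, and one that needs treatment is Grade 4. Treated torsades is therefore Grade 4.
4. **Consequence.** Steps 2 and 3 give a related Grade 4 event. Set side by side:

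| | Section 4.6.1 | Table 1, footnote a | Section 5.1.3.2 |
|---|---|---|---|
| Trigger | Related Grade 4 event | QT row met, no clear alternative cause | Drug-related toxicity |
| First step | Discontinue | Discontinue | Suspend |
| Resumption | Excluded (permanent) | Allowed in rare circumstances, with conditions | Allowed on clear improvement |
| Grade limit | Grade 4 | None | None |

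5. **Precedence.** Section 4.3.2 sends sites to Section 5.1.3 for interruption and discontinuation. Within it, 5.1.3.1 points to 4.6.1 and 5.1.3.3 points to Table 1. Section 5.1.3.4 is silent on permanence. No text says that 4.6.1 overrides the footnote, or that the event-specific table qualifies 4.6.1.
6. **Exposed group.** About 100 Cohort A patients are randomized 1:1, so 100 / 2 = 50 receive azithromycin. The maximum is 48 weeks × 7 days = 336 doses, which matches Section 4.3.2.1. The documents give no torsades incidence, so no expected count can be derived.

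**The case against.** The best defense is that the rules can be obeyed together. Section 4.6.1 is mandatory and the footnote only permits, so a site that never resumes where 4.6.1 applies breaks neither. The footnote would still have work to do: Appendix 5 has no QT-interval row, the two QTcF-threshold rows need not be Grade 4, and the third row also covers other ECG findings. Section 5.1.3.1 names 4.6.1 as the place for discontinuation. Section 5.1.3.4 calls for cardiology advice, and if that work-up finds another cause the event may cease to be related, so that resumption would not conflict with 4.6.1.

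Much of this stands, and it narrows the point. It does not remove it. The harmonizing reading is reasonable but unwritten, and a reader could equally hold that the specific table qualifies the general list. Discussion with the Medical Monitor does not fill the gap either: 4.6.1 gives no discretion once its trigger is met, and Section 9.2 rules out prospective requests to deviate.

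Several stronger inferences are tempting and are not supported:

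- *The instructions are opposite for any torsades episode.* Both begin with discontinuation, and an untreated episode can be Grade 2 or 3.
- *One site could stop permanently and another rechallenge, both fully compliant.* Section 4.6.1 binds every site, so resuming after a related Grade 4 event would breach it.
- *Table 2 makes torsades Grade 4 because it is life-threatening.* The entry "Life-threatening; extreme limitation in activity; significant assistance required" applies only to events not listed in the WHO scale, and Appendix 5 has a cardiac rhythm row.
- *Other sections already bar resumption.* Section 5.1.2.10 lists "Known prolongation of the QT interval, a history of torsades de pointes, congenital long QT syndrome, bradyarrhythmias or uncompensated heart failure" under the word contraindications, but asks physicians to weigh the risk and states no prohibition. The exclusion "History of congenital or documented QT prolongation" governs entry, not continuation.
- *Torsades is the most dangerous azithromycin event, or the discontinuation summaries will be distorted.* The documents rank no events and name other potentially fatal ones. Section 6.5 summarizes adverse events leading to discontinuation, and no effect on that summary is shown.

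**Conclusion.** The conflict is real and narrow. For a torsades episode that needs treatment and has no clear alternative cause, Section 4.6.1 makes the stop permanent, while footnote a, and on its wording Section 5.1.3.2, leave resumption open. The disagreement is about permanence alone.

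The conclusion assumes that torsades is graded on the Appendix 5 cardiac rhythm row and that the investigator follows the Table 3 default on relatedness. It does not reach episodes below Grade 4 or episodes later attributed to another cause. The number of patients affected is probably very small, although the documents do not allow an estimate. The case for acting rests on the potential seriousness of each event and the low cost of clarifying the text. It implies no view on which rule is clinically right.

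**What to change.** Reconcile Sections 4.6.1, 5.1.3.2, 5.1.3.3 (Table 1 footnote a) and 5.1.3.4. State:

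- to which of the three QT rows, and to which grades, footnote a applies;
- whether Section 4.6.1 overrides footnote a and Section 5.1.3.2 for related Grade 4 events.

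Use the same wording in each place. The sponsor's safety physicians decide which rule stands.

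The protocol already shows that this kind of alignment is practical. The hearing rule is a permanent stop in Sections 4.5.5, 4.6.1 and 5.1.2.7, and its Table 1 row carries no resumption footnote.

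The cost is a few sentences in the next amendment, with no new visit, procedure or data item.
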